### 2.4. Study Objectives

#### Study Objectives and Endpoints

##### Part 1 (Dose escalation) Primary Objective

- To assess safety and tolerability at increasing dose levels of PF-06647263 administered as an intravenous (IV) infusion every 3 weeks (Q3W) and weekly (QW) in patients with advanced solid tumors unresponsive to currently available therapies, or for whom no standard therapy is available, in order to estimate the Maximum Tolerated Dose (MTD) and select the Recommended Phase 2 Dose (RP2D).

##### Secondary Objectives

- To evaluate the overall safety profile;
- To characterize the single and multiple dose pharmacokinetics (PK) of PF-06647263, total antibody, and unconjugated payload;
- To evaluate the immunogenicity of PF-06647263;
- To document preliminary evidence of anti-tumor activity based on response rate (RR).

CCI [REDACTED]

[REDACTED]

[REDACTED]

##### Part 2 (Expansion) Primary Objective

- To confirm safety and tolerability and explore preliminary evidence of anti-tumor activity of PF-06647263 based on response rate (RR) at the RP2D in patients with previously treated metastatic TNBC and advanced platinum-resistant OVCA which express EFNA4.

## Secondary Objectives

- To evaluate the overall safety profile at the RP2D;
- To characterize the single and multiple dose PK of PF-06647263, total antibody, and unconjugated payload;
- To evaluate the immunogenicity of PF-06647263;
- To document preliminary evidence of anti-tumor activity based on progression free survival (PFS) and overall survival (OS).

CCI [REDACTED]

[REDACTED]

[REDACTED]

## Endpoints

### Primary Endpoint (Part 1)

- First cycle Dose Limiting Toxicities (DLTs) in order to determine the MTD and RP2D.

### Primary Endpoint (Part 2)

- Response rate (RR) as determined by the Response Evaluation Criteria in Solid Tumor (RECIST) version 1.1 criteria.

### Secondary Endpoints (Parts 1 and 2)

- Adverse Events as characterized by type, frequency, severity (as graded by NCI CTCAE v.4.03), timing, seriousness and relationship to study therapy;
- Laboratory abnormalities as characterized by type, frequency, severity (as graded by NCI CTCAE v.4.03) and timing;
- Vital Sign abnormalities;
- Systemic PK exposure of PF-06647263, total antibody, and unconjugated payload will be determined with validated methods. Standard noncompartmental PK parameters will be determined from the respective concentration-time data;

- Immunogenicity of PF-06647263; Human serum ADA (anti-PF-06647263 antibody) samples will be analyzed for the presence or absence of anti-PF-06647263 antibodies, following a tiered approach using screening, confirmation and titer/quantitation;
- Objective tumor response, as assessed using RECIST version 1.1 by calculating the Overall Response Rate (ORR), Clinical Benefit Response Rate (CBRR), Progression Free Survival (PFS), and Overall Survival (OS)-Part 2 only.

CCI [REDACTED]

[REDACTED]

[REDACTED]

### **3. INTERIM ANALYSES, FINAL ANALYSES AND UNBLINDING**

No interim analysis or blinding is planned for this study. The final analysis will be conducted after the last subject last visit (LSLV).

### **4. HYPOTHESES AND DECISION RULES**

#### **4.1. Statistical Hypotheses**

There are no statistical hypotheses. The emphasis of the final analyses will be on estimation of key summary statistics.

#### **4.2. Statistical Decision Rules**

##### **4.2.1. Part 1**

Decision rules are based on calculating unit probability mass (UPM) of three dosing intervals corresponding to under, proper, and over dosing in terms of toxicity. Specifically, the underdosing interval is defined as  $(0; pT - e1)$ , the over-dosing interval  $(pT + e2)$ , and the proper-dosing interval  $(pT - e1, pT + e2)$ , where  $e1$  and  $e2$  are small fractions. For a target DLT rate of 0.25, the target equivalence interval is  $(0.20, 0.30)$ . The three dosing intervals are associated with three different dose-escalation decisions (Table 1). The under-dosing interval corresponds to a dose escalation (E), over-dosing corresponds to a dose de-escalation (D), and proper-dosing corresponds to remaining at the current dose (S). Given a dosing interval and a probability distribution, the unit probability mass (UPM) is defined as the ratio of the probability of the interval to the length of the interval. Once the safety assessment is complete for Cycle 1, the focus will be on allocation of new subjects to the dose most likely to be an MTD.

The study continues accruing until one of the three stopping conditions below is triggered. The algorithm will stop if any of the following criteria is met:

1. The maximum sample size has been achieved.

2. MTD has been identified with sufficient accuracy: at least 9 patients have been accumulated on a dose that is currently estimated to be the MTD, or
3. All doses explored appear to be overly toxic and the MTD cannot be determined.

Specifically the mTPI approach formalizes stopping rules as follow:

Rule 1 (early termination): if the first dose is too toxic  $\rightarrow \Pr(p_1 > p_T / \text{data}) > \xi$  ;  $\xi = 0.975$

Rule 2 (dose exclusion), if dose=  $i$  is too toxic  $\rightarrow \Pr(p_i > p_T / \text{data}) > \xi$  ;  $\xi = 0.975$   
then exclude doses  $\geq i$

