### 2.2. MTD Determination (Part 1)

A modified toxicity probability interval method (mTPI) targeting a DLT rate of 25% with an equivalence interval (20%-30%) will be utilized in order to estimate MTD. Patients will be enrolled in cohorts of 2 to 4, starting with 0.015 mg/kg for the first cohort. Subsequent dose levels may include a maximum 100% escalation until either the dose is  $\geq 0.060$  mg/kg, a patient experiences a DLT or Grade 2 thrombocytopenia considered related to PF-06647263

after which, dose escalation in subsequent cohorts will follow a modified Fibonacci scheme with maximum dose increases of 67%, 50%, 33%, 33%. Table 1 illustrates the possible dose levels when the Modified Fibonacci scheme is initiated at the 3rd dose level. Intermediate dose levels to further evaluate the safety and/or PK may be evaluated following discussion between Sponsor and Investigator.

	Modified Fibonacci^ scheme starts from dose level 3	Modified Fibonacci^ scheme starts from dose level 2	Modified Fibonacci^ scheme starts from dose level 1
Dose Level	Dose (mg/kg Q3W)	Dose (mg/kg Q3W)	Dose (mg/kg Q3W)
-1	0.01	0.01	0.01
1 (Starting dose)	0.015	0.015	0.015
2	0.030	0.030	0.025
3	0.060	0.050	0.038
4	0.100	0.075	0.050
5	0.150	0.100	0.067
6	0.200	0.134	0.089
7	0.267	0.178	0.119
8		0.238	0.158
9			0.211

The modified toxicity probability interval (mTPI) design uses a Bayesian decision-theoretic framework and a beta/binomial hierarchical model to tailor dose-escalation and de-escalation decisions. These rules are conceptually similar to those used by the 3+3 design and all the dose-escalation decisions for a given trial can be pre-calculated under the mTPI design and presented in a two-way table.

The decision rules to “dose escalate” (E), “no change in dose” (S), “dose de-escalate” (D) or “dose de-escalate, unacceptable toxicity” (U) are described below:

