**Table 1. Decision Rules**

Number	Number of Patients treated at a Dose level											
	DLT	n=2	n=3	n=4	n=5	n=6	n=7	n=8	n=9	n=10	n=11	n=12
0	E	E	E	E	E	E	E	E	E	E	E	E
1	D	S	S	S	E	E	E	E	E	E	E	E
2	U	D	D	S	S	S	S	S	S	S	S	S
3		U	U	D	D	S	S	S	S	S	S	S
4			U	U	U	D	D	D	D	D	D	S
5				U	U	U	U	U	D	D	D	D
6					U	U	U	U	U	U	U	D
7						U	U	U	U	U	U	U

Cohorts of patients could receive doses already tested but a dose that is associated with decision “Dose de-escalate, unacceptable toxicity” cannot be revisited and no more patients should be treated at this dose or higher doses for the remainder of the trial.

A minimum of 9 patients treated at the MTD dose is required to establish such dose as the RP2D. The maximum sample size would be N=70 but actual sample size will depend on the underlying dose toxicity profile and variability in actual data realization. The initial dosing regimen tested in Part 1 will be PF-06647263 administered once every 3 weeks (Q3W) consistent with the pre-clinical toxicity study. Evaluation of a weekly (QW) regimen will be initiated when the first patient treated with the Q3W regimen experiences a DLT or Grade 2 thrombocytopenia related to study treatment. The starting dose of the QW regimen will not exceed one-third of the highest Q3W dose evaluated. Once initiated, the 2 regimens will be evaluated in parallel and independently based on the same dose-escalation criteria as described above.

Dose escalation will stop under any of the following conditions:

1. The maximum sample size has been achieved;
2. At least 9 patients have been accumulated at a dose that is predicted to be the MTD;
3. All doses explored appear to be overly toxic and the MTD cannot be determined.

### 2.3. Part 2

Upon identification of the MTD, approximately 30 patients will be enrolled at the MTD in order to explore benefit from treatment as suggested by preclinical findings and will better define the safety profile at the RP2D. This expansion component aims at evaluating ADC (PF-06647263) at the MTD in two cancer indications:

- a. Previously treated metastatic TNBC which expresses EFNA-4 (15 patients).
- b. Advanced epithelial ovarian cancer, primary peritoneal or fallopian tube cancer (OVCA) which expresses EFNA-4 and which has progressed or relapsed during or within 6 months post most recent therapy with a platinum agent (15 patients).

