### **5. SAMPLE SIZE DETERMINATION**

Similar to the conventional 3+3 design, the exact sample size of the mTPI design in Part 1 cannot be pre-specified in advance because it is a dynamic feature of the design. The minimum sample size after which the Part 1 can be stopped and MTD declared is 9. If two dose regimens are evaluated, the maximum sample size would be 70 patients.

As for the number of subjects treated at each dose, it is expected that the typical number will be 2-4 subjects for the doses actually studied. For the dose declared as MTD at the end of trial, this number will be at least 9. However, since variable cohort size is allowed, the actual number of subjects treated at each dose will vary from 2 to 12. For example, N=12 is achieved if 4 additional patients are enrolled in a cohort of n=8.

The sample size in Part 2 is based on clinical considerations, rather than statistical justification. It will include 30 subjects in two cohorts of tumor types of interest (ie, TNBC and OVCA) to confirm the safety and tolerability of the recommended dose based on Part 1 and to assess preliminary anti-tumor activity.

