### **7.2.2. MTD Definition**

The MTD would be any doses with true toxicity probabilities in the Equivalence Interval (EI) where the EI is defined as [20%-30%].

In practice, the MTD will be the highest dose associated with the occurrence of DLTs  $\leq 33\%$  (eg, 3/9 evaluable patients experience a DLT during the first treatment cycle).

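### Table 1 prints de-escalate at 4/10, 4/11 and 5/12, where the mTPI rule it is said to implement gives stay

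*SAP*

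**What the plan says.** Section 2.2 describes an mTPI design "targeting a DLT rate of 25% with an equivalence interval (20%-30%) will be utilized in order to estimate MTD". The design "uses a Bayesian decision-theoretic framework and a beta/binomial hierarchical model", and the SAP adds that "all the dose-escalation decisions for a given trial can be pre-calculated under the mTPI design and presented in a two-way table". Table 1 is that table, with rows for 0 to 7 DLTs and columns for 2 to 12 patients.

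Section 4.2.1 gives the rule behind it. UPM is the probability of an interval divided by its length. Under-dosing maps to E, proper dosing (0.20 to 0.30) to S and over-dosing to D. A dose is excluded (U) when the posterior probability that its DLT rate exceeds 0.25 is above 0.975. The link to the table is explicit: "The three dosing intervals are associated with three different dose-escalation decisions (Table 1". The SAP does not give the beta prior, does not write that the interval with the largest UPM decides, and does not say how ties are resolved. Nothing in it says that any cell was altered from the algorithm's output.

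Section 5 sets the patient numbers at which an MTD is declared: "For the dose declared as MTD at the end of trial, this number will be at least 9". It adds: "For example, N=12 is achieved if 4 additional patients are enrolled in a cohort of n=8". Section 7.2.2 gives a separate criterion based on the observed rate: "In practice, the MTD will be the highest dose associated with the occurrence of DLTs" at or below 33%, with 3/9 as its example.

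**The concern.** If Table 1 is the pre-calculated output of the rule in 4.2.1, each cell should follow from that rule. Three cells in the 10-to-12-patient columns do not.

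The cells can be reached with the permitted cohorts of 2 to 4. One DLT in 4 patients (S), then two in the next 4, gives 3/8 (S), and rule and table agree at both steps. Eight patients are too few to declare an MTD, so another cohort follows. One DLT in 2 more patients gives 4/10, one in 3 gives 4/11, and two in 4 gives 5/12. At each of these the rule says stay and the table says de-escalate.

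DLTs are the Part 1 primary endpoint and Table 1 governs decisions on them. As written, the same data have two answers in the SAP.

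**Working it through.** **Inputs.** From 2.2 and 4.2.1: target 0.25, intervals (0, 0.20), (0.20, 0.30) and (0.30, 1), exclusion threshold 0.975. Two assumptions are needed because the SAP is silent: a Beta(1,1) prior, varied below, and the largest UPM deciding.

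**Formulas.** With x DLTs in n patients and prior Beta(a, b), the posterior is Beta(a+x, b+n−x), with distribution function F.
- Under-dosing UPM = F(0.20)/0.20
- Proper-dosing UPM = [F(0.30) − F(0.20)]/0.10
- Over-dosing UPM = [1 − F(0.30)]/0.70
- U if 1 − F(0.25) > 0.975

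**Reproducing the plan's table.** For n = 2, 3, 4, 5 and 6 there are 3 + 4 + 5 + 6 + 7 = 25 possible cells. For n = 7 to 12 there are 6 × 8 = 48. The total is 73. Reading columns by their headings, Beta(1,1) reproduces 68, including all U cells. The mismatches are 1/6, 4/10, 4/11, 4/12 and 5/12.

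**The three cells under Beta(1,1).**

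| Cell | Posterior | Under | Proper | Over | Rule | Table 1 |
|---|---|---|---|---|---|---|
| 4/10 | Beta(5,7) | 0.0504/0.20 = 0.25 | 0.1599/0.10 = 1.60 | 0.7897/0.70 = 1.13 | S | D |
| 4/11 | Beta(5,8) | 0.0726/0.20 = 0.36 | 0.2038/0.10 = 2.04 | 0.7237/0.70 = 1.03 | S | D |
| 5/12 | Beta(6,8) | 0.0300/0.20 = 0.15 | 0.1354/0.10 = 1.35 | 0.8346/0.70 = 1.19 | S | D |

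**Does the layout explain it?** The copy of Table 1 that was read has twelve body columns under eleven patient-number headings (n=2 to 12). This was treated as a conversion fault. Each of the twelve columns was dropped in turn, and 4/10, 4/11 and 5/12 disagreed every time. 4/12 (printed D, rule S: 2.47 v 0.94) disagrees only when columns are read by the headings, so it is not counted as firm.

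**Does another prior explain it?** Beta(0.7,0.5) gives proper v over of 1.59 v 1.12, 2.03 v 1.03 and 1.35 v 1.19, again S in all three. So do Beta(0.5,0.5), Beta(0.005,0.005), Beta(0.25,0.75) and Beta(0.5,1.5). A search over 182,709 priors (a from 0.001 to 6, b from 0.001 to 12) never fell below 4 mismatches by the headings: the three cells plus 4/12. If one of the last patient-number columns is taken as a duplicate, the minimum is 3, and these are always the three cells. By the headings, a prior that makes 5/12 D costs at least 5 mismatches elsewhere; for 4/10 the cost is at least 10, for 4/11 at least 22, and for all three together at least 22. In a separate grid of 12,100 priors, none that made all three D kept the printed S at 2/5, 3/7 or 3/8.

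**Where the unstated items change a cell.** 1/6 is printed E. Beta(1,1) gives S (under 2.12 v proper 2.47), but Beta(0.7,0.5) gives E (2.36 v 2.28). At 1/2, Beta(1,1) gives an exact tie between S and D (1.12 each) and the table prints D, so a tie rule is also needed.

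**The case against.** The best case for the table has four parts.

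- **Stay has little practical content here.** Section 5 caps a dose at 12 patients and cohorts are 2 to 4. No further cohort fits at 5/12 or 4/11, and only one cohort of 2 fits at 4/10. This stands as a limit on the consequence. It does not remove the conflict, because stopping rule 2 in 4.2.1 turns on whether a dose with at least 9 patients is currently estimated to be the MTD, and S and D point different ways on that.
- **The 33% criterion in 7.2.2 sides with the table.** The observed rates are 40%, 36% and 42%, so the D entries may be a deliberate override. That is possible, but the SAP does not say so and does not link 7.2.2 to Table 1. The criterion does not explain the grid either, since Table 1 prints S at 3/7 (43%) and 3/8 (37.5%).
- **The rule was completed by assumption.** This is fair, and 5/12 is the thinnest of the three: Beta(1,0.5) gives D (1.16 v 1.23), as does Beta(2,2) (1.13 v 1.24). Those priors do not rescue the table. Read by the headings, Beta(2,2) mismatches 15 of 73 cells, including 0/2, 0/3 and 0/4.
- **The prior may be in the protocol.** It may, and its absence from the SAP alone would be only missing detail. The point rests on the grid not following from the rule, under any beta prior tested.

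**Conclusion.** The point holds and should be fixed. Three of 73 cells (4/10, 4/11, 5/12) contradict the rule in 4.2.1 whatever the column alignment. Read by the headings, 5 of 73 differ under a uniform prior and 4 of 73 under the best-fitting beta priors. The result assumes a beta prior and that the largest UPM decides, which the interval-to-decision mapping implies but does not state. The 4/10 and 4/11 margins are wide; 5/12 is narrower and more prior-dependent.

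The reach is limited. The three cells need 10 or more patients on one dose, and in each the table is the stricter side. The effect on MTD selection is not quantified, because it depends on DLT curves that the SAP does not give.

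Two weaker observations depend on unresolved readings: 1/6 turns on the prior, and 4/12 on the column alignment. If 4/12 is D, it also sits awkwardly with 7.2.2, since 4/12 is the same observed rate as that section's 3/9 example. The two passages serve different steps, however: next-cohort assignment and final MTD definition.

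**What to change.** In 4.2.1, state the beta prior parameters, that the interval with the largest UPM decides, and how ties are resolved. Then do one of two things: regenerate Table 1 from that rule, or keep the printed grid, list every cell that departs from the rule on purpose, and describe the design as a modified mTPI. Reconcile 2.2, Table 1, 4.2.1 and 7.2.2 so that the same counts lead to one decision, and say how the 33% criterion relates to the UPM rule. Which decision applies in each cell is for the sponsor to settle.

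The cost is SAP wording and a few minutes of computation, with no extra patients.

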#### **4.2.2. Part 2**

Part 2 of this study is intended to confirm the safety and tolerability of the dose selected in Part 1 while assessing the antitumor activity of PF-06647263 in patients with solid tumors. The DLT rate and analyses of concordance and confidence interval may be estimated.

Analyses may be performed on data from both Part 1 and Part 2 to explore the relationships between PK parameters, safety endpoints, and efficacy endpoints.

### **5. SAMPLE SIZE DETERMINATION**

Similar to the conventional 3+3 design, the exact sample size of the mTPI design in Part 1 cannot be pre-specified in advance because it is a dynamic feature of the design. The minimum sample size after which the Part 1 can be stopped and MTD declared is 9. If two dose regimens are evaluated, the maximum sample size would be 70 patients.

As for the number of subjects treated at each dose, it is expected that the typical number will be 2-4 subjects for the doses actually studied. For the dose declared as MTD at the end of trial, this number will be at least 9. However, since variable cohort size is allowed, the actual number of subjects treated at each dose will vary from 2 to 12. For example, N=12 is achieved if 4 additional patients are enrolled in a cohort of n=8.

The sample size in Part 2 is based on clinical considerations, rather than statistical justification. It will include 30 subjects in two cohorts of tumor types of interest (ie, TNBC and OVCA) to confirm the safety and tolerability of the recommended dose based on Part 1 and to assess preliminary anti-tumor activity.

### **6. ANALYSIS SETS**

Several analysis sets are defined and will be considered for this study.

#### **6.1. Full Analysis Set**

The full analysis set includes all enrolled patients. This is equivalent to the ITT (intent-to-treat) population.

## **6.2. 'PER PROTOCOL' Analysis Set**

Part 2: the per protocol (PP) analysis sets includes all enrolled patients (for each indication) who receive at least one dose of study medication and who do not have major treatment deviations during first cycle.

Specifically: Patients with major treatment deviations in Cycle 1 are not evaluable for the RP2D assessment and therefore will not be included in the PP analysis. Major deviations include failure to satisfy major entry criteria (eg, confirmation of the target disease; signed informed consent) or use of other anticancer treatments during the active treatment and disease follow-up phases other than as defined/allowed in this protocol. At least one baseline and one post-baseline disease assessment are required for the PP analysis.

Modified PP analysis sets may be considered for additional analyses and would include patients enrolled either in Part 1 or in Part 2.

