## 6.8. Protocol Deviations

All deviations will be listed in the CSR. Major treatment deviations include, but are not limited to, less than 80% of the planned Cycle 1 PF-06647263 dose provided the reduction/omission is not due to treatment-related toxicity. Subjects with major Cycle 1 treatment deviations are not evaluable for MTD.

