### **9.2. Statistical Analyses**

#### **9.2.1. Primary Analysis**

Dose Limiting Toxicity (DLT) is the primary endpoint of the dose escalation component of the study, which will be summarized by dose level using the Per Protocol Analysis Set for patients in the dose escalation portion of the study. A listing of the DLTs will also be provided.

If necessary, a summary and listing of the DLT by malignancy may be provided using the Per Protocol Analysis Set for patients in the MTD expansion portion of the study.

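### DLT rates are summarised in a Per Protocol set that can be read to drop a dosed patient who had a DLT because an entry criterion failed

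*SAP*

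**What the plan says.** Section 6.2 opens its definition with "Part 2: the per protocol (PP) analysis sets includes all enrolled patients (for each indication) who receive at least one dose of study medication" and requires that there be no major treatment deviation in the first cycle. It then states the consequence: "Patients with major treatment deviations in Cycle 1 are not evaluable for the RP2D assessment and therefore will not be included in the PP analysis". The next sentence gives examples: "Major deviations include failure to satisfy major entry criteria (eg, confirmation of the target disease; signed informed consent". It also names unpermitted anticancer treatment, and the paragraph ends by requiring a baseline and a post-baseline disease assessment. Nothing in 6.2 treats a patient who had a DLT differently.

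Section 6.8 gives the matching rule for the MTD: "Subjects with major Cycle 1 treatment deviations are not evaluable for MTD". Its list is open: "Major treatment deviations include, but are not limited to, less than 80% of the planned Cycle 1 PF-06647263 dose". The under-dosing example carries a condition: "provided the reduction/omission is not due to treatment-related toxicity".

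Section 9.2.1 uses the Per Protocol set for the Part 1 DLT summary by dose level, which is the primary analysis. For the expansion cohorts it says: "If necessary, a summary and listing of the DLT by malignancy may be provided using the Per Protocol Analysis Set".

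Section 6.3 defines the Safety Analysis Set as enrolled patients who received at least one dose. Section 9.2.3 summarises adverse events in that set, with Cycle 1 shown separately.

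**The concern.** Failing an entry criterion does not undo exposure. A patient dosed in the TNBC or OVCA cohort whose tumour type is later not confirmed still received the drug and was still observed through Cycle 1. Section 7.2.1 defines a DLT by adverse events in that cycle and makes no reference to tumour type. Part 1 pools advanced solid tumours to estimate the MTD, so the plan itself treats tolerability as informative across tumour types. Target-disease confirmation and the post-baseline disease assessment belong to an efficacy set, yet the same set carries the DLT summary.

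The SAP guards against losing toxicity in one place. Under 6.8, a dose cut made because of treatment-related toxicity is not a deviation. The entry-criterion exclusion has no similar guard.

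What is at stake is the reported DLT rate. It is the primary analysis in Part 1. In Part 2 it bears on the primary objective in section 2.4 of confirming safety and tolerability, and section 2.1 allows Part 2 safety information to change the dose recommended for later trials. The study is open label, so nothing in the design stops eligibility from being judged after toxicity is known. The SAP gives no sign that this is intended or expected.

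**Working it through.** The SAP states no figure on this point, so there is none to reproduce. The check is a reading of the sections, followed by simple proportions.

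**Reading the sections together**

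1. Which set carries the DLT rate? Section 9.2.1: the Per Protocol set, in both parts.
2. How is that set defined? Only in 6.2, labelled Part 2 and organised by indication. No Per Protocol set is defined for Part 1. The modified sets mentioned at the end of 6.2 are only a possibility for additional analyses.
3. Does 6.2 exclude entry-criterion failures? It moves from major *treatment* deviations in Cycle 1 to major deviations, and lists entry failures under the second term. The two sentences are consecutive and explain the same exclusion, so reading them as one rule is natural but not forced.
4. Is there an exception for a DLT? None in 6.2. The one in 6.8 covers only under-dosing.

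**Size of the effect**

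Let x be the number of DLTs among n patients.

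- Removing one patient with a DLT gives (x − 1)/(n − 1), a fall of (n − x)/[n(n − 1)].
- Removing one patient without a DLT gives x/(n − 1), a rise of x/[n(n − 1)].

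*Expansion cohort*, n = 15 (sections 2.1 and 2.3), with x = 4 assumed for illustration:

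- All dosed patients: 4/15 = 26.7%.
- One DLT patient removed: 3/14 = 21.4%. The fall is 11/(15 × 14) = 11/210 = 5.2 percentage points.
- One patient without a DLT removed: 4/14 = 28.6%. The rise is 4/210 = 1.9 points.

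*MTD criterion*, which section 7.2.2 sets at a DLT occurrence of at most 33%, with 3/9 evaluable patients as its example. This case applies only if the reading in 6.2 carries over to MTD evaluability through the open list in 6.8:

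- All dosed patients, 4 DLTs in 10 assumed: 4/10 = 40%, above the limit.
- One DLT patient removed: 3/9 = 33.3%, which is the SAP's own example of meeting it.
- In the other direction, 3/10 = 30% with one patient without a DLT removed becomes 3/9 = 33.3%.

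**The case against.** The best defence is that 6.2 is a Part 2 definition and an entry failure is not a treatment deviation. The Part 2 label and the change of wording are real, so 6.2 is ambiguous and is not a clear instruction to discard DLTs. But 9.2.1 applies a Per Protocol set to Part 1 and no other definition exists. Nor does 6.2 give another route by which the listed entry failures could matter. Two programmers could build different DLT denominators from this text.

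A second defence is that the toxicity is not lost. This is correct. The patient stays in the Safety Analysis Set and the event appears in the Cycle 1 adverse event tables. It drops out only of the DLT rate.

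A third is that no prespecified Part 2 decision depends on the rate. The expansion DLT summary is optional, section 4.1 sets no hypotheses, and there is no Part 2 DLT threshold, so moving from 26.7% to 21.4% crosses nothing. Section 2.1 also does not restrict the safety information used for the dose to Per Protocol patients. All of this stands. It limits the consequence in Part 2 to a distorted estimate.

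A fourth is that the bias can go either way, because ineligible patients without a DLT are removed too. That also stands.

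A reader might go further and infer that the exclusion would change escalation decisions, since taking out one DLT patient moves to a different cell of the decision table in section 2.2. The SAP does not support this. That table counts patients treated at a dose level, decisions follow once the Cycle 1 safety assessment is complete, and no text feeds the Per Protocol set into it. The 9.2.1 summary belongs to the final analysis, which section 3 places after the last patient's last visit.

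**Conclusion.** The point holds as a defect in how the reported DLT rate is defined. Under a natural reading of 6.2, a dosed patient with a Cycle 1 DLT can leave both numerator and denominator because the target disease was not confirmed.

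One such patient in a cohort of 15 with four DLTs lowers the rate by 5.2 points, from 26.7% to 21.4%. If the same reading reaches MTD evaluability through 6.8, one patient can move 4/10 = 40% to 3/9 = 33.3%. The second figure is conditional, because 6.8 does not name entry failure and its list is merely open. Target-disease confirmation is also an example that fits the two expansion cohorts better than the mixed tumours of Part 1.

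The DLT counts are assumed, and the SAP gives no expected number of ineligible patients; the event is probably uncommon. It would be wrong to conclude that the SAP always understates toxicity, hides the event, or alters escalation. The conclusion rests on the SAP alone.

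**What to change.** - **6.2:** limit the entry-criterion exclusion to the efficacy Per Protocol analyses, and use one term throughout in place of the two kinds of deviation.
- **9.2.1:** summarise DLTs in a DLT-evaluable set, defined for each part from Cycle 1 exposure and observation in line with 6.8. Keep dosed patients with a Cycle 1 DLT when the failed criterion is target-disease confirmation. Apply the same rule to those without a DLT who meet the exposure and observation requirement, so that inclusion does not depend on the outcome.
- **6.8:** state whether entry failure affects MTD evaluability, so that the open list does not settle it by default.
- **Other entry criteria:** some may bear on toxicity risk. Show the DLT rate with and without patients who failed them.
- **Missing consent:** handle it separately, as a question of whether the data may be used.
- **Listing:** list entry violations separately.

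The cost is SAP wording and, where such patients exist, one further presentation of the DLT rate. The downside is that a few patients outside the target tumour type stay in the toxicity denominator.
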